5.3. Rationale for this Study Design and Dose Selection

CRV431 has consistently demonstrated the ability to prevent the progression of liver fibrosis in a variety of animal models and in precision-cut human liver slices. The primary mechanism of action to prevent collagen synthesis is via Cyp B inhibition although additional mechanisms may involve Cyp A and Cyp D. The half maximal inhibitory concentration (IC₅₀) for cyclophilin inhibition ranges from 3.2 to 9.5 ng/mL. Human whole blood concentrations after a single dose 75 mg of CRV431 achieved a maximum observed whole blood concentration (C_{max}) of 334 ± 106 ng/mL. Steady state concentrations for 75 mg QD dosed for 28 days achieved a C_{max} of 1397.5 ± 97.8 ng/mL with a mean trough level of 889.5 ± 70.4 ng/mL demonstrating that whole blood concentrations are above the cellular IC₅₀ range for the entire dosing period which ensures target engagement. In order to evaluate the potential dose response of CRV431 on safety and NASH biomarkers, a second dose of 225 mg QD demonstrating a steady-state C_{max} of 1844 ± 321.9 ng/mL will be explored.

The use of AST and Pro-C3 have been increasingly used to identify fibrosis progression in NASH subjects. Aspartate aminotransferase has been used to stratify patients as a sole indicator or as an integral part of NASH scoring systems. Type III collagen neo-epitopes (Pro-C3) has emerged as a biomarker indicative of active fibrogenesis. Given that the primary pharmacological mechanism of CRV431 is to directly influence the rate of fibrogenesis, Pro-C3 and AST are known biological indicators of active fibrogenesis. The use of these biomarkers in the inclusion criteria for subject selection ensures subjects have active disease with fibrogenesis. Both markers provide a more adequate assessment of disease activity than serial measurements of liver transaminases alone. Given the duration of the study and the sample size of this Phase 2a trial, it is essential to enrich the study design by including patients with active fibrogenesis. While serial transaminases measurements, repeated 3 to 4 weeks apart can indicate disease progression, transaminases lack the specificity provided by AST and Pro-C3. Thus, an inclusion criterion of AST >20 IU/L combined with a Pro-C3 >15.5 ng/mL precludes the need for multiple pre-Screening liver enzyme testing ([Schuppan D, et al., 2018](#)).

5.4. Risks and/or Benefits to Subjects

This is the first study of CRV431 in subjects with presumed NASH F2/F3 fibrosis. As this is a Phase 2a trial designed to evaluate safety, PK and biomarkers of fibrosis, subjects who participate in this study are not expected to derive any clinical benefit over the course of the 28-day study. Subsequently, liver biopsies for entry are not required.

Currently, there is no standard of care for NASH patients although life-style intervention including weight loss and alterations in diet are routinely recommended with bariatric surgery for overweight patients (see American Association for the Study of Disease Guidelines for NAFLD). Nonclinical studies conducted by the sponsor to support the Investigational New Drug (IND)

[REDACTED]

[REDACTED]

6. STUDY OBJECTIVES

6.1. Primary Objectives

- To evaluate the safety and tolerability of QD 75 mg and 225 mg doses of CRV431 in presumed NASH F2/F3 subjects compared to placebo control over 28 days of dosing;
- To evaluate the PK of a QD dose of CRV431, its major metabolites and fraction unbound in presumed NASH F2/F3 subjects over 28 days of dosing.

6.2. Secondary Objective

- To evaluate non-invasively the antifibrotic activity of a QD dose of CRV431, as measured by quantification of selected biomarkers of fibrosis, in presumed NASH F2/F3 subjects over 28 days of dosing.

6.3. Exploratory Objectives

- To generate exploratory data regarding the antifibrotic activity of a QD dose of CRV431 over 28 days of dosing by performing hepatic evaluations via laboratory assessments of biomarkers [REDACTED]

- [REDACTED]
- [REDACTED]
- [REDACTED]
- [REDACTED]
- [REDACTED]

- ALT and/or AST decrease from baseline.

6.4. Study Endpoints

6.4.1. Safety Endpoints

Safety and tolerability parameters, including AEs, SAEs, AEs of special interest, physical examinations including weight and height, concomitant medications, laboratory assessments including blood chemistry, hematology and coagulation, urinalysis, pregnancy screening, ECG, and vital sign assessments, will be determined.

6.4.2. Pharmacokinetic Endpoints

The PK parameters for CRV431 in whole blood will be determined in subjects in fasted state. A list of PK parameters is shown in [Table 5](#).

On an exploratory basis, concentration-effect relationships will be explored between CRV431 whole blood concentrations and all biomarkers measured. Subject demographics and clinical laboratory data will be evaluated as potential covariates in PK/PD model using non-linear mixed effect modeling with direct and indirect models.

[REDACTED]

7. INVESTIGATIONAL PLAN

7.1. Overall Study Design

This is a randomized, single-blind, placebo-controlled, QD dose study of CRV431 in presumed NASH F2/F3 subjects. This study will consist of 3 phases: (i) Screening and Randomization; (ii) treatment; and (iii) follow up.

7.1.1. Screening and Randomization Period

Screening visits will be conducted within 30 days prior to study Day 1. During the Screening Phase, each potential subject will provide informed consent prior to starting any study-specific procedures.

Due to the logistics and time needed for the retest of the [REDACTED], for those subjects that an investigator requests a retest of these samples, as described in Section 8.2, the screening period may be extended an additional 30 days for a screening period of up to 60 days total in order to allow subjects who are waiting the retest results the opportunity to meet all study entry criteria.

Once a subject is considered eligible, prior to Day 1, a concomitant medication form will be completed by the site and sent to the sponsor for approval. See Section 7.4.1 for prohibited medications.

Subjects who are eligible will be randomized as described in Section 7.3.3 and as shown in Table 2.

Table 2: Study Design

Cohort*	Fibrosis Stage	N	Day 1 – 28, fasted oral dosing	Day 29 - 42
A	F2/F3	12	CRV431 75 mg	Observation/Follow up
B		6	Placebo ^a	
C		12	CRV431 225 mg	
D		6	Placebo ^b	

*Randomized assignment; 2:1 – CRV431:Placebo

^a Matching Placebo for Cohort A - 75 mg dose.

^b Matching Placebo for Cohort C - 225 mg dose.

Potential study subjects who meet all inclusion and exclusion criteria for this study, but who, for personal or administrative reasons, are not included in the study may be re-screened if more than 30 days has passed since their previous screening. For these subjects, use of [REDACTED] results previously obtained for this study will be extended for an additional 30 days up to a total of 60 days. There are no restrictions on the number of re-screens permitted.

Potential study subjects who previously screened and failed only [REDACTED] but met all other inclusion criteria and met none of the exclusion criteria for this study may be re-screened.

7.1.2. Treatment Period

Subjects will receive treatment with CRV431 or matching placebo from Day 1 to Day 28. Study visit days that include treatment administration occur on Days 1, 2, 7, 14, and 28. Visit windows will be allowed and are as follows: Day 7 and Day 14, the visit window is ± 1 day and Day 28 the visit window is $+ 2$ days. If the study visit for Day 28 is extended, the subject must continue taking study drug until the visit is completed.

Whole blood samples will be collected pre-dose and through Day 42 or early termination for safety and PK assessments as shown in [Table 3](#) and [Table 6](#), respectively. AEs will be collected as described in [Section 11.4](#).

7.1.3. Follow Up Period

After completion of the treatment period, the subjects will be monitored for additional 14 days. A visit window of ± 2 days will be allowed for the Day42/EOS visit.

Subjects who do not complete the study may be replaced within a dosing cohort, unless a stopping rule precludes replacement. Safety criteria for dose adjustments or stopping rules are provided in [Section 7.5](#).

The overall study design of all scheduled procedures is shown in [Table 3](#).

Table 3: Schedule of Events

Procedure	Screening (Day -30 to -2)	Day -1	Day 1	Day 2	Day 7 (±1)	Day 14 (±1)	Day 28 (+2)	EOS/ Day 42 (±2)	ET ^a
Informed Consent ^b	X								
Demographics	X								
Weight and height	X								
HIV, HBV, HCV tests	X								
Physical exam	X								
Medical history	X								
Inclusion/exclusion	X	X							
Randomization		X							
Pregnancy test ^c	X	X						X	X
FSH	X								
Drugs of abuse and alcohol screen	X	X							X
Vital signs ^d	X	X	X	X	X	X	X	X	X
ECG ^e	X	X	X	X	X	X	X	X	X
Blood chemistry ^f	X	X	X	X	X	X	X	X	X
Hematology and Coagulation	X	X	X	X	X	X	X	X	X
Urinalysis	X	X	X	X	X	X	X	X	X
PK ^g			X			X	X		X ^h
Fraction Unbound ^g			X				X		
ELF Score	X						X		

^k On Day 1 and Day 28, subjects will fast overnight for at least 8 hours, will take CRV431 or matching placebo and will fast for an additional 2 hours following receipt of study drug. On subsequent days subject will fast overnight for at least 8 hours, will take CRV431 or matching placebo and will fast for an additional 30 minutes following receipt of study drug.

7.2. Number of Subjects

A total of 36 adult male or female subjects with presumed NASH F2/F3 will be enrolled. Of the 36 subjects, 12 subjects will be enrolled in Cohort A to receive 75mg of CRV431, 6 subjects will be enrolled in Cohort B to receive the matching placebo of Cohort A, 12 subjects will be enrolled in Cohort C to receive 225mg of CRV431 and 6 subjects will be enrolled in Cohort D to receive the matching placebo of Cohort C.

7.3. Treatment

Subjects in Cohort A will receive CRV431 75 mg (1 x 75 mg softgel capsule) QD and subjects in Cohort B will receive the matching placebo (1 x placebo softgel capsule) for Cohort A.

Subjects in Cohort C will receive CRV431 225 mg (3 x 75 mg softgel capsules) QD and subjects in Cohort D will receive the matching placebo (3 x placebo softgel capsules) for Cohort C.

7.3.1. Treatment Administration

Subjects will take study drug on the morning of each dosing day, with approximately 240 mL of water. On Day 1 and Day 28, subjects will fast overnight for at least 8 hours, will take CRV431 or matching placebo and will fast for an additional 2 hours after treatment administration. On subsequent days, subject will fast overnight for at least 8 hours, will take CRV431 or matching placebo and will fast for an additional 30 minutes after treatment administration. On visit days, the exact time of dosing will be decided based on logistics and will be documented in the source documents.

7.3.2. Treatment Compliance

While in the Clinical Research Unit, study treatment will be administered under the supervision of site personnel. Compliance during the non-study visit days will be assessed by subject reporting and pill count. Study personnel should counsel subjects on study medication compliance during each study visit. A qualified designee will be responsible for monitoring the administration of the timed oral doses on study visit days.

7.3.3. Randomization and Blinding

Upon determination that a subject meets all eligibility criteria, the subject will be randomized on Study Day -1 to receive either CRV431 or matching placebo in a 2:1 subject ratio (12 CRV431 75mg to 6 matching placebo and 12 CRV431 225mg to 6 matching placebo) in accordance with a computer-generated randomization schedule generated by a non-study statistician. Using this randomization schedule, pharmacy staff or designee will assign treatment sequentially to each eligible subject within a given cohort.

This is a single blind study where the investigator and sponsor are unblinded. However, the subject is blinded and will not know if he or she will receive CRV431 or matching placebo.

7.4. Study Restriction

7.4.1. Prohibited and Concomitant Medication

Any prescription medication or over the counter medication taken from 30 days prior to the time of consent to the End of Study/Early Termination Visit will be recorded in the subject's medical record (source document) and Case Report Form (CRF).

Once a subject is considered eligible, prior to Day 1, a concomitant medication form will be completed by the site and reviewed by the sponsor for approval.

Use of the following medication prior to and during the study is prohibited:

- Any drugs or substances known to be strong inhibitors or inducers of CYP3A4/5 and drugs whose major elimination pathway is via the BSEP or OAT3 transporters, and drugs that are major substrates of the hepatic uptake transporters OATP1B1 and OATP1B3 received within 30 days prior to the first dose of study drug. (**NOTE:** Please refer to [Appendix A](#) and if there are questions, please contact the sponsor);
- Systemic immunosuppressants, with the exception of short-term treatment for asthma, received within 6 months prior to the first dose of study drug and during the study;
- Any investigational product or investigational device received within 30 days prior to the first dose of study drug and during the study.

For questions regarding the use of medications, the investigator should contact the sponsor for further discussion. In case of an acute medical emergency, discussion with the Sponsor is excluded and the subject should be treated according to the judgement of the PI.

Consumption of foods and beverages containing the following substances will be prohibited as indicated:

- Xanthines/caffeine: 24 hours prior to dosing and throughout the period of PK sample collection;
- Alcohol: 48 hours prior to dosing and throughout the period of PK sample collection;
- Grapefruit/Seville orange: 14 days prior to dosing and throughout the period of PK sample collection.

7.4.2. Meals

On Day 1 and Day 28, subjects will fast overnight for at least 8 hours, will take CRV431 or matching placebo and will fast for an additional 2 hours after administration of study drugs. On subsequent days, subject will fast overnight for at least 8 hours, will take CRV431 or matching placebo and will fast for an additional 30 minutes after administration of study drugs.

7.5. COVID-19 Vaccine

Hepion in no way wishes to preclude subjects from receiving the COVID-19 vaccine. However, in order to minimize potential adverse events associated with the vaccine, if possible, the subject should try to receive their second dose of the vaccine seven days prior to the commencement of receiving study drug (Day 1) or receive their first dose of the vaccine 96 hours after their last dose on Day 28.

Enrolled study subjects who have an opportunity to be vaccinated against COVID-19 should do so. Study subjects will be permitted to continue on the study if they receive the COVID-19 vaccine.

The COVID-19 vaccine should be recorded in the subject's Concomitant Medications CRF page if the subject receives the vaccine after consent and through Day 42/EOS.

7.6. Data Safety Monitoring Board

An independent Data Safety Monitoring Board (DSMB) will monitor the trial. The DSMB will comprise of medical professionals with expertise in NASH and clinical trials and are external to the Sponsor. The DSMB will meet periodically or as needed to review accumulating safety data and any available PK data collected throughout the trial.

Safety and available PK data will be reviewed by the DSMB prior to proceeding with the next higher dose cohort. The DSMB will review safety data when at least six (6) subjects in Cohort A (CRV431 75 mg) and at least three (3) subjects in Cohort B (matching placebo) have reached 28 days of dosing, as described in Section 12.3.1. The DSMB will also review the Day 28 safety data from the remaining subjects to confirm there are no changes to the prior safety assessment.

The roles and responsibilities will be further defined in a Charter.

7.7. Safety Criteria for Adjustment or Stopping Doses

7.7.1. Individual Subject Criteria

If any of the criteria below are met by an individual subject, then no further dosing will occur at any of the study sites until a review of all available safety information is performed by the DSMB, Medical Monitor, and Sponsor. Appropriate Regulatory Agencies and Ethics Committees will be informed as applicable. If it is later determined that further dosing can be performed safely then an application for a substantial protocol amendment will be submitted to the appropriate Regulatory Agencies and Ethics Committees, if applicable. Stopping criteria for an individual subject includes:

- Grade 3 or higher CTCAE AEs possibly or probably related to study drug as determined by the investigator and sponsor;
- Grade 4 CTCAE AEs regardless of relation to study drug as determined by the investigator and sponsor;
- Any SAEs thought to be related to the study drug as determined by the investigator and sponsor.

For subjects experiencing any hepatic AEs or SAEs judged by the investigator or sponsor to be related to study drug, the investigator, DSMB, Medical Monitor and Sponsor will review all available safety data and make a determination to proceed with one of the following options:

- If the event was a drug-induced liver injury (DILI), considered as increases in aminotransferases (AT) $>3 \times$ ULN or $>3 \times$ baseline where baseline is defined as the average values of Screening and Day -1, no additional subjects will be dosed until it is determined that it is safe to proceed and in addition the frequency of blood chemistries will increase to daily, if appropriate.

- Repeat testing of ALT, AST, ALP, TBL will be performed within 48-72 hours to confirm the abnormality.
- If there are persistent elevations of AT > 3 x ULN or a 2-fold increase above baseline values (for those subjects with elevated values prior to drug exposure) upon repeat testing then close observation visits should be implemented and/or discontinuation of drug should be considered. Close Observations are described in Section 7.8.
- If the event was not a DILI, as defined above, one of the following actions will be taken:
 - Dose an entire additional cohort at the same or lower dose than the dose taken by the subject that experienced the event in question;
 - Continue to pause the study, until it is determined, that it is safe to proceed.

A decision to discontinue or temporarily interrupt the study drug for a subject will be considered based on following criteria:

- If ALT/AST baseline measurements (BLM) are <2 x ULN, discontinue if ALT or AST increases to >5 x BLM;
- If ALT/AST BLM \geq 2 x ULN but <5 x ULN, discontinue if ALT or AST increases to 3 x BLM;
- If ALT/AST BLM \geq 5 x ULN, discontinue if ALT or AST increases to >2 x BLM AND the increase is accompanied by a concomitant increase in TBL to >2 x BLM OR the International Normalized Ratio (INR) concomitantly increases by >0.2;
- Any subjects with signs and symptoms of fatigue, nausea, vomiting, right upper quadrant pain or tenderness, fever, and/or rash, accompanied by a >5% increase in eosinophils;
- Subjects who miss more than 2 consecutive QD doses of study drug. Subjects may be replaced unless a stopping rule precludes replacement.

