7.7.2.1. Study Stopping Criteria

Study will be stopped and a review of all available safety information is performed by the DSMB, Medical Monitor, and Sponsor if any of the below criteria is met:

- ≥ 1 subject develops a Grade 5 CTCAE adverse event attributed to CRV431
- ≥ 2 subjects develop a Grade 4 CTCAE adverse event attributed to CRV431
- ≥ 3 subjects develop the same Grade 3 CTCAE adverse event attributed to CRV431

The study may be restarted depending on the specific AE, relationship to the study drug and with the agreement of the DSMB, Medical Monitor and Sponsor.

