7.7.3. Pharmacokinetic Criteria for Dose Adjustment

Dose adjustment is not available for subjects in Cohort A receiving 75 mg of CV431 QD. If a patient demonstrates adverse events that trigger the need for stopping, that patient will be stopped and an additional patient will be started on the same dose unless the study data indicates a problem with the dose level as recommended by the DSMB. Subjects in Cohort C, receiving 225 mg of CRV431 QD, experiencing a drug exposure related Grade 3,4 or 5 CTCAE can have a dosage reduction to 150 mg of CRV431 once daily.

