8.3. Subject Withdrawal Criteria

8.3.1. Early Termination of Subjects from the Study

Subjects who discontinue the study should complete all scheduled safety assessments at the Early Termination Visit. If an Early Termination Visit and a scheduled visit coincide, procedures for both visits should be completed, without duplication. Subjects must discontinue the study for the following reasons:

- Subject withdraws consent;
- Subject unwilling or unable to follow study procedures, per judgment of the investigator;
- Investigator, sponsor, or Regulatory Authority judge that further dosing with study drug would be harmful to the subject;
- Subject experiences an SAE that is judged, by the investigator and the sponsor, to be related to study drug;
- Subject experiences a Grade 3 CTCAE AE judged, by the investigator and the sponsor, to be related to study drug;
- Subject experiences a Grade 4 CTCAE AE judged, by the investigator and the sponsor, regardless of the relation to study drug;
- Subject experiences a Grade 3 or Grade 4 CTCAE laboratory abnormality judged by the investigator and the sponsor, to be related to study drug except for asymptomatic elevations in cholesterol or triglycerides which are accepted;

- Subject with normal ALT and bilirubin at baseline who experiences confirmed, non-cholestatic ALT $>3 \times$ ULN and bilirubin $>2 \times$ ULN OR subjects with elevated ALT at baseline who experiences confirmed, non-cholestatic ALT $>10 \times$ baseline value and bilirubin $>2 \times$ ULN;
- Subject experiences a confirmed,
 - QTcF interval 500 msec;
OR
 - QTcF interval change from baseline ≥ 60 msec that has an absolute value ≥ 480 msec. The value of an individual ECG time point is the average of the triplicate values
 - “confirmed” is defined as the abnormality duplicated, at least 1 hour after the abnormality is first noted, by the results of a set of 3 ECGs performed in triplicate, at least 5, but not more than 10 minutes between each assessment;
- Subject experiences any hepatic AE or SAE judged by the investigator or sponsor as DILI and to be related to study drug and not to the subject’s underlying NASH.

Subjects who discontinue the study due to the safety stopping criteria will be replaced if the investigator and sponsor agree and the criteria outlined in Section 7.5 are not violated. Subjects who discontinue the study for non-safety reasons may be replaced.

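### Section 7.7.1 automatically pauses dosing for an unrelated Grade 4 event but not for an unrelated Grade 5 event, and 7.7.3 permits a dose reduction where 8.3.1 requires discontinuation

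*Combined protocol and SAP*

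**What the plan says.** **Halt rules.** If one subject meets a criterion in protocol 7.7.1, "no further dosing will occur at any of the study sites until a review of all available safety information is performed". The reviewing parties are the DSMB, the Medical Monitor and the Sponsor. Three criteria are listed:

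- The first covers "Grade 3 or higher CTCAE AEs possibly or probably related to study drug as determined by the investigator and sponsor", and so depends on causality.
- The second covers "Grade 4 CTCAE AEs regardless of relation to study drug as determined by the investigator and sponsor", and so sets causality aside.
- The third covers an SAE of any kind, provided it is believed to be drug-related.

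A hepatic rule follows in the same section. For a drug-induced liver injury judged related, "no additional subjects will be dosed until it is determined that it is safe to proceed". Section 7.7.2 adds study-level rules, and 7.7.2.1 stops the study if at least one "subject develops a Grade 5 CTCAE adverse event attributed to CRV431".

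**Dose reduction.** Section 7.7.3 says that Cohort C subjects "experiencing a drug exposure related Grade 3,4 or 5 CTCAE can have a dosage reduction to 150 mg of CRV431 once daily". Section 8.3.1 opens its list with "Subjects must discontinue the study for the following reasons". That list includes a related Grade 3 AE, a Grade 4 AE whatever its cause, and a related SAE. It has no exception for Cohort C.

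**The concern.** The first 7.7.1 bullet covers Grade 3 and everything above it. The second drops the causality condition but names one grade only. Read literally, a non-fatal Grade 4 event that nobody attributes to the drug stops dosing everywhere, while a death that nobody attributes to the drug need not. The protocol gives no reason for being stricter about the lesser event.

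Whether a death pauses dosing automatically therefore rests on a causality judgement by the investigator and sponsor, both of whom know the treatment (7.3.3). Bullet 2 removes that dependence for Grade 4 but not for the grade above it. There is a knock-on effect. The synopsis ties a DSMB safety review to stopping criteria being met, and 12.3.1 makes the opening of Cohort C conditional on no stopping rule having been met. An unrelated death would meet neither description, which leaves DSMB agreement as the remaining safeguard on escalation.

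The second issue is a permission that has not been reconciled with a mandate. After a related Grade 3 or 4 AE in Cohort C, 7.7.3 points to 150 mg and 8.3.1 points to withdrawal. Those who decide how dosing restarts would have two answers.

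**Working it through.** No statistical figure bears on this point, so the check sets the rules against two hypothetical events, each in one subject and each judged unrelated.

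| Halt rule | What it requires | Unrelated Grade 4 | Unrelated Grade 5, never recorded as Grade 4 |
|---|---|---|---|
| 7.7.1, bullet 1 | Grade 3 or above, possibly or probably related | not met | not met |
| 7.7.1, bullet 2 | Grade 4, any relationship | **met** | not met |
| 7.7.1, bullet 3 | SAE, related | not met | not met |
| 7.7.1, hepatic rule | hepatic event, related | not met | not met |
| 7.7.2, SAE, AE and laboratory rules | at least 3 subjects, related | not met | not met |
| 7.7.2, QTcF rule | at least 3 subjects with a confirmed ECG finding | not met | not met |
| 7.7.2, liver injury rule | 1 subject, related | not met | not met |
| 7.7.2.1, all three rules | attributed to CRV431 | not met | not met |

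The QTcF rule is the only other one that does not ask about causality, and a single death cannot meet it. If the fatal course had first been entered as a separate Grade 4 AE, bullet 2 would already have fired. The gap is therefore confined to deaths recorded only as Grade 5.

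For the dose-reduction issue, take a Cohort C event that is related through drug exposure.

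| Event | 7.7.1 | 7.7.3 | 8.3.1 |
|---|---|---|---|
| Grade 3 AE | all-site halt | reduction permitted | must discontinue |
| Grade 4 AE | all-site halt | reduction permitted | must discontinue |
| Grade 5 AE | all-site halt (also 7.7.2.1) | reduction named, but impossible | no practical meaning |

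The 7.7.1 column matters. If the event is judged possibly or probably related, bullet 1 has already stopped dosing everywhere. The two sections therefore collide when dosing resumes after the joint review, which may itself need a substantial amendment.

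**Reach of a pause, if Grade 5 is added to bullet 2** (cohort sizes from 7.2, interim trigger from 12.3.1, before replacements):

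- Before Cohort C opens: 12 + 6 = 18 subjects at most.
- After it opens: at least 6 + 3 = 9 subjects have reached 28 days, so at most 36 − 9 = 27.
- The missed-dose item in 7.7.1 covers "Subjects who miss more than 2 consecutive QD doses of study drug". That means 3 or more doses, and 3/28 = 10.7% of the course.

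**The case against.** The strongest reply on the first issue is that very little escapes. Under 11.3, any valid reason to suspect a link, even an undetermined one, makes an event related, and possible relatedness is enough for bullet 1. A death is an SAE and reaches the sponsor within 24 hours (11.5). The DSMB can meet as needed (7.6), and 7.9 allows a halt for serious or unexpected risk. The 7.7.1 list is introduced by a word that may leave it open-ended, and the DSMB charter is not available. The sponsor also wrote a Grade 5 rule in 7.7.2.1 and tied it to attribution, so declining to halt every site for, say, an accidental death could be deliberate. All of this stands as narrowing. It does not explain why an unrelated Grade 4 event should halt dosing when an unrelated Grade 5 event does not, and the routes in 7.6 and 7.9 are discretionary.

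On the second issue, a reader might infer that a site could rely on 7.7.3 to keep a subject on 150 mg by its own decision. The documents do not support that, because the all-site halt and the joint review come first. It is also true that a site which always discontinues breaches neither section. But 7.7.3 contrasts Cohort A, where the patient is stopped, with Cohort C, where the dose may be lowered. That suggests reduction was meant as a real alternative, so 8.3.1 cannot simply be assumed to override it.

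A reader might also infer that asymptomatic cholesterol or triglyceride elevations give 7.7.3 a conflict-free use. The exemption sits only in the laboratory-abnormality bullet of 8.3.1. The Grade 3 and Grade 4 AE bullets carry no such exemption, and 11.2.1 allows an abnormal laboratory finding to be an AE. The exemption does not clearly free 7.7.3 from conflict.

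**Conclusion.** Both mismatches hold and should be fixed.

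First, a Grade 5 event judged unrelated and never recorded as Grade 4 triggers no automatic pause in the protocol text, while an unrelated Grade 4 event does. The likeliest explanation is a drafting omission. The gap is narrow, and no likelihood of such a death is estimated here. It would be too strong to conclude that the trial could not be paused after an unrelated death. It could be, at the discretion of the DSMB or the sponsor.

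Second, 7.7.3 and 8.3.1 give incompatible directions for related Grade 3 and 4 AEs in Cohort C, and the Grade 5 part of 7.7.3 cannot operate. The conflict affects decisions on resuming treatment after review.

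The conclusion assumes that Grade 5 means death, since CTCAE v5.0 is adopted but its table is not reproduced, and that the charter does not already supply the missing trigger. The ordering anomaly between Grades 4 and 5 does not depend on the first assumption.

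**What to change.** **7.7.1:** insert *or higher* after Grade 4 in the second bullet, and align the DSMB charter if it repeats the rule. The Grade 4 wording in 8.3.1 can stay, because a deceased subject cannot discontinue.

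**7.7.3:** delete Grade 5 and limit the reduction to events that do not require discontinuation under 8.3.1. If reduction after a related Grade 3 or 4 event is intended, add a matching Cohort C exception to 8.3.1 instead. That choice belongs to the sponsor and the DSMB.

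**Cost:** a few words by protocol amendment. In operation, an unrelated death would pause dosing at all sites, within the bounds worked out above. A pause of 3 doses or more could affect Day 28 PK and could bring subjects under the missed-dose item. The protocol does not say whether a study-imposed pause counts as missed doses, and that item only asks for discontinuation or interruption to be considered. An unrelated Grade 4 event already carries the same cost, and an unrelated death should be rare with 36 subjects dosed for 28 days.
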